9.3. Efficacy Analysis

The per-protocol population will be the primary population for analysis of all efficacy objectives. Efficacy objectives will also be assessed using the modified intent-to-treat (mITT) populations. Subgroup analyses will be performed on both the per-protocol and the mITT populations.

All analyses for the SSI endpoints assume 100% correct classification of suspected *S aureus* cases, ie, no cases are missed and no noncases are included in the statistical analysis. All primary and secondary efficacy analyses will be repeated for sex, race, ethnicity, and age subgroups.

9.3.1. Efficacy Analysis Populations

Two analysis populations are defined: per-protocol and mITT. To be included in the per-protocol efficacy population, a subject must meet all eligibility criteria, be vaccinated as randomized, undergo the index surgery 10 to 60 days after vaccination, undergo surgery consistent with study-defined criteria for the index surgery, have no major protocol violations prior to reporting of the suspected *S aureus* infection, and have no infection or malignancy identified at the index surgical procedure. To be included in the mITT population, a subject must be vaccinated and undergo spinal surgery. For both populations, subjects will be assigned to the investigational product to which they were randomized (SA4Ag or placebo).

9.3.2. Analysis of the Primary Endpoint

For the primary objective, the efficacy of SA4Ag will be based on the number of per-protocol subjects in each vaccine group with postoperative *S aureus* BSI and/or deep incisional or organ/space SSI occurring within 90 days of elective open posterior spinal fusion procedures with multilevel instrumentation, as confirmed by the EAC. In case of multiple occurrences meeting the primary endpoint from the same subject, only the first episode will be used to calculate the VE.

Examples of the estimated efficacy and associated CIs for a selected number of SA4Ag cases are presented in Table 15.

Table 15. Estimated Efficacy and Associated Confidence Intervals for a Select Number of SA4Ag Cases

Analysis Stage	Total Cases	SA4Ag Cases	Estimated Efficacy and Confidence Interval ^a	Comments
Futility	10	7	-133% (-1298%, 46.7%)	Conditional power <20%; possible futility declaration
	15	9	-50% (-412%, 52.3%)	Conditional power <20%; possible futility declaration
	24	11	15.4% (-105%, 66%)	Conditional power <20%; possible futility declaration
Interim	24	3	85.7% (24.9%, 99.0%)	Max number of SA4Ag cases that permits inference that true VE is >20%

Table 15. Estimated Efficacy and Associated Confidence Intervals for a Select Number of SA4Ag Cases

Analysis Stage	Total Cases	SA4Ag Cases	Estimated Efficacy and Confidence Interval ^a	Comments
Final	48	8	80.0% (56.5%, 91.9%)	Estimated efficacy = 80%
	48	11	70.3% (40.3%, 86.4%)	Estimated efficacy =70%
	48	14	58.8% (21.0%, 79.6%)	Max number of SA4Ag cases that permits inference that true VE is >20%

Abbreviations: N/A = not applicable; VE = vaccine efficacy.

- a. 99.7% confidence level for interim analysis; 95.1% confidence level for final analysis; 95% confidence level for futility.

The findings at the time of the final analysis will serve as the primary basis for efficacy conclusions.

9.3.2.1. Supplementary Analysis

After completion of the final protocol analysis, additional cases may be identified and submitted for adjudication. Cases collected after the final analysis (ie, overrunning - Whitehead, 1997)⁶¹ will be included in supplementary descriptive analyses using 95% CIs (as the final number of events is unknown); these analyses are supplementary and provided for completeness.

9.3.3. Analysis of Secondary Endpoints

9.3.3.1. Efficacy

All secondary endpoints will be analyzed using the per-protocol population. The binomial methodology described above will be used to test the null hypothesis of no difference between treatments, with $p = 1/2$ and number of trials set to total number of cases from SA4Ag and placebo. Two-sided p-values of the probability of the indicated SA4Ag cases or fewer will be calculated.

As sensitivity analyses, the secondary endpoints will be evaluated in the mITT populations with $p = 1/2$ and number of trials set to total number of cases from SA4Ag and placebo.

Secondary endpoints will be analyzed only after all subjects have completed the study and the database is locked.

9.3.4. Analysis of Exploratory Endpoints

9.3.4.1. Immunogenicity Analysis

The immunogenicity endpoints are the results from antigen-specific functional assays (OPA assay for CP5 and CP8, and cLIA antibody titers for ClfA and MntC). Additional exploratory assays to measure immune responses may be conducted on all 4 antigens. Assay titers will be obtained at each applicable visit.

The immunogenicity baseline will be Visit 1.

Windows for obtaining blood samples are:

- Visit 1: up to 7 days prior to vaccination.
- Visit 2 (index hospital admission): day of surgery blood sample collection any time from admission up to but before the index surgical procedure.
- Visit 2 (index hospital admission): day of discharge blood sample collection: up to 3 days before discharge, but must be after index surgical procedure.
- Visits 4 and 5: ± 7 days.
- Visit 6: -2 to +12 days.

There are no windows for unscheduled blood sample collections.

Missing assay results are not to be replaced or imputed.

The number and proportion of subjects achieving threshold values will be determined at each scheduled time point for each vaccine group. Two-sided 95% CIs will be calculated. Threshold values will be specified in the SAP.

Geometric mean titers (GMTs), geometric mean fold rises (GMFRs) relative to baseline (Visit 1), and the proportion of subjects who achieve specific thresholds to the SA4Ag antigens, as well as their corresponding 95% CIs, will be compiled at each visit by vaccine group. Antigen-specific immunoglobulin and OPA titers will be logarithmically transformed prior to analysis. Within each vaccine group and for each antigen separately, GMTs at each visit will be calculated. Two-sided 95% CIs will be constructed by back transformation of the CIs for the mean of the logarithmically transformed assay results computed using the Student t distribution.

Two-sided 95% CIs for the GMFR at each postvaccination blood draw visit will be constructed by back transformation of the CIs for the mean of the logarithmically transformed fold rise on the assay data computed using the Student t distribution.

In addition, GMTs and CIs will be estimated from an analysis of covariance (ANCOVA), also computed using the logarithmically transformed assay results. The model terms will be treatment, site, visit, baseline assay value, and treatment-visit interaction. 'Visit' for the index hospital admission will be partitioned into 'day of surgery' and 'day of discharge.' The difference between least squares (LS) means for SA4Ag minus placebo will be exponentiated to obtain a ratio of the geometric means. The corresponding 2-sided 95% CIs will be obtained.

For sensitivity purposes, the ANCOVA will be repeated by adding 1 factor and its interaction at a time, eg, add sex and treatment-sex interaction to the model. This will be performed for

sex, race, age group, baseline colonization status, and other subgroups as specified in the SAP. Significant interactions of subgroups with treatment, defined as $p < 0.10$, will be examined further for synergistic and antagonistic effects.

The proportions of subjects achieving n-fold rises from baseline to each postbaseline visit will be compiled, as well as their 95% CIs. N-fold rises will be 2-, 4-, 8-, 16-, and 32-fold.

Reverse cumulative distribution curves (RCDCs) will be generated to present the immunogenicity data at baseline and the Day 42 postoperative assessment time point. RCDCs may be repeated, but limited to cases.

All immunogenicity analyses will be performed in the per-protocol and mITT populations, but limited to subjects with at least 1 postvaccination assay value. It is anticipated that the immunogenicity analyses will be conducted following database lock; however, an interim immunogenicity analysis may be performed on a subset of subjects, if these results are required to support regulatory agency interactions to expedite the clinical development of SA4Ag.

If an interim immunogenicity analysis is performed, it will be limited to subjects who have at least 1 valid and determinate postvaccination assay value. The interim analysis will be limited to group-level statistics and will be conducted by an unblinded team, independent of the sponsor, in order to maintain blinding. All immunogenicity endpoints are defined as exploratory and the study will not be prematurely terminated or altered in any way (eg, no design or operational changes) from the interim immunogenicity analysis; therefore, no type I error adjustment is proposed.

9.3.4.2. Colonization Analysis

Windows for obtaining colonization swabs will be the same as for immunogenicity. Colonization swabs at Visit 2 (index hospital admission) will be collected both on admission and again, prior to discharge.

Baseline colonization status is defined as:

- Positive for any subject with at least 1 positive *S aureus* colonization swab at either Visit 1 or Visit 2 (admission sample only) or both.
- Negative for any subject with all negative *S aureus* colonization swabs at both Visit 1 and Visit 2 (admission sample only) and no missing colonization swabs.
- Missing for subjects without any colonization swab results from either Visit 1 or Visit 2 (admission sample only) or subjects with any combination of negative colonization swabs and at least 1 missing colonization swab.

At each postsurgery time point, the proportions of colonization swabs testing positive for *S aureus* at each anatomical site and the RR between the 2 vaccine groups along with its exact 2-sided 95% CI will be obtained. Subgroup compilations will be performed based on

age group, sex, baseline colonization status, and primary endpoint status (ie, case or noncase). Statistical significance of treatment-subgroup interactions will be obtained from logistic regression. The logistic regression will include treatment, subgroup, and treatment-subgroup interaction. One subgroup will be examined at a time. Some subgroups may be combined to achieve reasonable sample size. Anatomical sites will be examined separately.

Analyses will be performed for the per-protocol and mITT populations, further limited to subjects having at least 1 nonmissing colonization swab value at any visit.

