### 6.3. Other Endpoints

#### 6.3.1. Demographic, Medical History, and Baseline Characteristics

Disposition variables will include enrolled, randomized, vaccinated, completed, and discontinued. Discontinuations will be split into reasons for discontinuation.

The demographic characteristics will include sex, race, racial designation (completed only if race = Asian), ethnicity, and age on the day of vaccination. Age on the day of vaccination will be derived in years ( $[\text{vaccination date} - \text{date of birth} + 1]/365.25$ ) and truncated to 0 decimal places. For subjects randomized but not vaccinated, the randomization date will be used instead of the vaccination date in the calculation of age.

Colonization status at baseline (Visit 1 or/and Visit 2 admission sample) will be compiled separately for each anatomical site (nose and throat), as well as “any anatomical site” (meaning both sites combined). The definition of colonization status when combining sites is described in [Section 8.1.4](#).

Body mass index (BMI), vital signs, colonization status at baseline, smoking status, alcohol consumption, and elapsed days from vaccination to index surgery will be summarized.

- BMI will be calculated as (weight [kg]/height [m] squared) and rounded to 1 decimal place.
- Vital signs include temperature (°C or °F), blood pressure (systolic and diastolic), pulse rate, and respiratory rate. All temperatures will be converted to °C.
- Alcohol consumption will be recorded as yes/no. If “yes,” then the number of units per week will be recorded.
- Elapsed days from vaccination to the index surgery will be the date of the index surgery minus the date of vaccination, plus 1.

Medical history data will be categorized according to the Medical Dictionary for Regulatory Activities (MedDRA) and summarized by vaccine group.

The Charlson Comorbidity Index (CCI) is a validated prognostic indicator for which factors, individually or in combination, may increase the risk of short-term mortality for subjects enrolled in longitudinal studies. On completion of the physical examination at Visit 1, the investigator will record the presence of each comorbid condition and age cohort as presented in [Table 5](#). The sum of the values for each comorbid condition is added to the subject’s value for age to obtain the CCI score. The 10-year mortality probability is calculated as  $0.983^{\text{EXP}[0.9 \times \text{CCI score}]}$  (Kastner et al).

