**Table 11. Operating Characteristics of Study Design**

Study Outcome	Assumed Vaccine Efficacy (%)			
	0%	20%	60%	70%
Futility				
at 10 cases	17.0%	9.6%	0.7%	0.2%
at 15 cases	15.7%	9.5%	0.7%	0.2%
at 24 cases	40.9%	34.3%	4.4%	1.0%
at any time	73.6%	53.3%	5.9%	1.4%
Positive Interim Analysis	0.0%	0.1%	5.8%	16.3%
Positive Final Analysis	0.3%	2.2%	54.7%	71.2%
Negative Final Analysis	26.1%	44.4%	33.6%	11.1%
Total Positive Outcomes	0.3%	2.3%	60.5%	87.5%
Total Negative Outcomes	99.7%	97.7%	39.5%	12.5%
Mean no. cases required	26.5	33.0	45.0	43.7

Percentages of study outcomes in 100,000 simulations of the trial under each assumed vaccine efficacy. ‘Positive’ outcomes are where the null hypothesis that VE ≤20% is rejected at either the interim or final analysis. ‘Negative’ outcomes are a declaration of futility or failing to reject the null hypothesis at the final analysis. All percentages rounded to 0.1%.

The analyses of the secondary endpoints, the exploratory efficacy endpoints, and the primary endpoint in the mITT efficacy population will be evaluated at a 2-sided alpha level of 0.05. The proportion of SA4Ag cases divided by total cases will be translated into VE for each endpoint. The upper and lower limits of the associated 95% CI on the proportion will be translated to upper and lower 95% confidence limits on VE.

Subgroup analyses will use the same methodology as described above, but will be performed separately at each level of the subgroup. Some levels of subgroups may be combined before analysis. Subgroups without cases in either vaccine group will not be analyzed.

The subgroup analyses on the primary endpoint from the PP efficacy population will be performed on the 24 cases (if the study ends on interim analysis) or 48 cases (if the study ends as planned). More PP cases may accumulate after the 24 or 48 cases as remaining subjects complete enrollment, so the subgroup analyses will also be repeated with the additional cases.

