#### **8.1.3.4. Colonization with *Staphylococcus aureus***

Colonization values obtained up to 7 days before vaccination until the day of admission for surgery will be considered eligible baseline values.

Colonization at each visit, acquisition, and clearance are binary endpoints, so they will be summarized with proportions. Vaccine groups will be compared using the CMH test. Site will be the stratification variable.

Carriage status will form a  $3 \times 2$  table with 3 categories—“persistent,” “intermittent,” and “noncarrier”—and 2 vaccine groups. “Indeterminate” will be considered a missing value. Vaccine groups will be compared using the CMH test. Site will be the stratification variable.

Subgroup analyses will be performed by executing logistic regressions with the dependent variable of the proportion of subjects colonized. The model terms will be vaccine group, subgroup, and vaccine group–subgroup interaction. The colonization results for subgroups with significant interactions, defined as  $p < 0.10$ , will be examined more closely.

One subgroup will be examined at a time. Anatomical sites will be examined separately. Only colonization at scheduled visits will be included. Only *S aureus* colonization will be analyzed because the purpose is to see if vaccine group has different effects within subgroup levels.

Vaccine groups will be compared using the Fisher exact test, 2-sided, for the proportion positive for *S aureus* from unscheduled visits. Stratification by clinical site is not proposed because the unscheduled visits will presumably be associated with possible BSI/SSI/ISA.

The number of these assessments per site should be low. Analyses will be performed by anatomical site and for anatomical sites combined.

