**8.1.4. General Considerations**

Day of surgery will be labeled Day 1. The day prior will be Day -1. However, in the analyses of local reactions and systemic events, the 10 days after vaccination will be referred to as Days 1-10.

All CIs for proportions will be 2-sided 95% intervals, obtained using the exact Clopper-Pearson method, as described by Agresti.

Performance of the van Elteren test will use modified ridit scores (Stokes et al).

Based on FDA recommendations, subgroup analyses will be performed for efficacy and selected immunogenicity analyses. The proposed subgroups will be defined by the following:

- Race
- Age group (18 to <50, 50 to 64, and 65 to <86 years)
- Sex
- Ethnicity (Hispanic/Latino and not Hispanic/Latino)
- Smoking status (current smoker, past smoker, and never smoked)
- Site (sites may be combined by similar rates of SSIs following surgery)
- Type of surgeon (as defined in [Section 6.3.2](#))
- Country
- CCI score substituting for medical history; CCI levels will be 0, 1, 2, and  $\geq 3$
- Colonization status at the time of surgery
- Colonization status at the time of vaccination
- Timing of surgery after vaccination (1-14 days, 15-30 days, 31-45 days, 46-64 days, and 65 days or more after vaccination)

Analyses with limited numbers of cases per subgroup may not be performed.

Colonization status at the time of surgery is defined as follows:

- Positive for any subject with at least 1 positive *S aureus* colonization swab at 1 anatomical site or both anatomical sites on the day of surgery
- Negative for any subject with negative *S aureus* colonization swabs at both anatomical sites and not more than 1 missing colonization result on the day of surgery
- Missing for subjects without any colonization swab results from either anatomical site on the day of surgery

The definition of colonization status for “any anatomical site” is the same for colonization at the time of vaccination and colonization on the day of surgery:

- Positive for any subject with at least 1 positive *S aureus* colonization swab at either anatomical site or both anatomical sites
- Negative for any subject with negative *S aureus* colonization swabs at both anatomical sites and not more than 1 missing colonization result
- Missing for subjects without any colonization swab results from either anatomical site

All statistically significant results associated with subgroup analyses will be regarded as hypothesis generating.

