### **8.2.1. Analyses for Efficacy**

All primary and secondary endpoints will be subjected to subgroup analysis, where SA4Ag and placebo will be compared at each level of the subgroup. Fifteen subgroups will be examined:

1. Race.
2. Age group.
3. Sex.
4. Ethnicity.
5. Smoking status.
6. Country.
7. CCI score.
8. Colonization at the time of surgery (performed for any *S aureus*).
9. Colonization at the time of surgery (performed for MRSA).
10. Colonization at the time of surgery (performed for MSSA).
11. Timing of the surgery after vaccination.

12. Presurgery decolonization (any/none).
13. Intrawound application of antibiotic (yes/no).
14. High-enrolling investigator sites (yes/no); the number of mITT subjects will be compiled by site. Sites with  $\geq 50$  mITT subjects will be considered high-enrolling sites.
15. High-attack rate investigator sites (yes/no); the number of mITT subjects with any PDI (BSI, deep incisional or organ/space SSI, superficial SSI, or ISA disease) will be compiled by site. The median of the nonzero values will be computed (only nonzero values will be included because multiple sites are expected to not have any PDI). Sites with the median or higher will be considered high-attack rate sites.

The subgroup analysis by timing of surgery after vaccination in the interval 1-14 days should be understood as an interval of 9-14 days in the PP efficacy population, because subjects with timing of 1-8 days after vaccination will be excluded from the PP efficacy population.

Subgroup analyses by site are not proposed because of the expected sparseness of cases.

Subgroup analyses will be performed in both the PP and mITT efficacy populations.

All analyses for 1 endpoint in 1 population, ie, all subjects plus every level of each subgroup, will be included in the same table.

Subgroup analyses will not be performed for postoperative ISA disease based on baseline *S aureus* colonization, because these are exploratory endpoints. Instead, baseline *S aureus* colonization will be included as a subgroup in the analyses of postoperative ISA disease.

Efficacy analyses are summarized in Table 14.

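### Baseline colonization status for the exploratory VE endpoints includes a post-vaccination swab, so VE from case counts alone depends on stratum sizes that the vaccine could change

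*Protocol*

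**What the plan says.** Protocol 2.4 sets two exploratory objectives for VE by baseline S aureus colonization, at 90 and at 180 days. Protocol 9.3.4.2 defines the status:

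- Positive: at least one positive "colonization swab at either Visit 1 or Visit 2 (admission sample only) or both".
- Negative: all swabs at both visits negative "and no missing colonization swabs".

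SAP 6.3.1 uses the same two visits, and SAP 8.1.3.4 states: "Colonization values obtained up to 7 days before vaccination until the day of admission for surgery will be considered eligible baseline values". Visit 1 is the vaccination visit. Surgery follows 10 to 60 days later (Protocol Section 3), or 9 to 90 days later in the SAP 5.2 per-protocol set.

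SAP 8.1.1 computes VE as 1 - p/(1 - p), where p is the SA4Ag share of all cases. No denominators enter. For subgroups it says: "Subgroup analyses will use the same methodology as described above, but will be performed separately at each level of the subgroup". The same section has an analysis with a ratio h of placebo to SA4Ag follow-up time, but SAP 8.1.1 and 8.2.1 limit it to the primary and secondary endpoints.

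The SAP's two subgroup lists differ. Section 8.1.4 includes "Colonization status at the time of vaccination" among the subgroups for efficacy. The fifteen efficacy subgroups in 8.2.1 omit it and give only surgery-time colonization (items 8 to 10: any S aureus, MRSA, MSSA).

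**The concern.** A stratum for a VE estimate should be fixed before the vaccine can act. Here one of the two swab occasions that set baseline status comes after vaccination. The plan itself treats carriage as something SA4Ag might change: Protocol 2.4 has an objective on colonization before and after SA4Ag, and SAP Table 25 explores vaccine effects on acquiring and clearing carriage.

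The case-count estimator equals one minus the relative risk only when both arms have the same number at risk in the stratum. Randomization gives that in expectation for strata set before vaccination. It does not for strata that the vaccine may alter. If fewer SA4Ag subjects become carriers before surgery, the SA4Ag arm has fewer baseline positives and more baseline negatives. Case counts then shift even if the risk per subject is the same in both arms. A reader could take the result as protection in carriers and none in noncarriers.

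**Working it through.** **Inputs**

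- Visit 1 carriage c: 20% to 50%, a general population range in Protocol Section 1.
- Allocation 1:1 (Protocol Section 3).
- Acquisition a from Visit 1 to admission among Visit 1-negative placebo subjects: 5%, 10%, 20%. Assumed; not in the documents.
- Relative reduction r of acquisition by SA4Ag: 30%, 50%, 80%. Assumed; not in the documents.
- Equal per-subject infection risk in both arms within each stratum, so that true within-stratum VE is 0. Assumed.

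**1. The plan's own figure.** For 14 SA4Ag cases of 48, VE = 1 - 14/34 = 58.8%. Clopper-Pearson limits on p at 95.1% give 21.0% to 79.6%. Both agree with Protocol Table 15, so the estimator is read correctly.

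**2. Formulas.** The share classed positive is P = c + (1 - c)a on placebo and V = c + (1 - c)a(1 - r) on SA4Ag. With equal risks, expected case-count VE is 1 - V/P in carriers and 1 - (1 - V)/(1 - P) in noncarriers. If V < P, the first is positive and the second negative.

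**3. Worked example (c = 30%, a = 10%, r = 50%).**

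- P = 0.30 + 0.70 x 0.10 = 0.370; V = 0.30 + 0.70 x 0.05 = 0.335.
- Carriers: 1 - 0.335/0.370 = +9.5%.
- Noncarriers: 1 - 0.665/0.630 = -5.6%.

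**4. Range over the 27 combinations, with c at 20%, 30%, 50%.**

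- Carriers: from +1.4% (c = 50%, a = 5%, r = 30%: 1 - 0.5175/0.525) to +35.6% (c = 20%, a = 20%, r = 80%: 1 - 0.232/0.360).
- Noncarriers: from -1.6% (a = 5%, r = 30%) to -20.0% (a = 20%, r = 80%). The result does not depend on c, because it reduces to -ar/(1 - a).

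**5. Clearance only.** A Visit 1-positive subject stays positive whatever Visit 2 shows, so faster clearance moves nobody and the error is 0. It does matter for the surgery-time subgroups. With c = 30%, a = 10% in both arms, and clearance of 20% on placebo and 30% on SA4Ag, P = 0.30 x 0.80 + 0.07 = 0.310 and V = 0.30 x 0.70 + 0.07 = 0.280. The errors are 1 - 0.280/0.310 = +9.7% and 1 - 0.720/0.690 = -4.3%.

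**6. With real protection.** If true VE is 50% in both strata, the step 3 inputs give 1 - 0.5 x 0.335/0.370 = 54.7% and 1 - 0.5 x 0.665/0.630 = 47.2%.

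**7. Sampling error.** A stratum with 12 of 24 cases on SA4Ag has a 95% CI for VE of -143% to 59%. With 24 carrier cases and true VE 0, the chance that the lower 95% limit exceeds 0 is 1.1% without the error. It is 2.1% with the step 3 inputs, 4.7% with c = 20%, a = 20%, r = 50%, and 11.0% if r is then 80%.

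**8. After the change.** Visit 1 strata have equal expected arm sizes, so the error is 0. For a post-vaccination stratum, 1 - hp/(1 - p) with h = placebo subjects/SA4Ag subjects also gives 0 in all 27 combinations. It does not remove selection. Suppose the vaccine has no effect on infection, and would-be acquirers keep a threefold risk (assumed) even when SA4Ag keeps them swab-negative. With the step 3 inputs, SA4Ag noncarrier cases are proportional to 0.630 + 0.035 x 3 = 0.735, against 0.630 on placebo. Case-count VE is 1 - 0.735/0.630 = -16.7%. With denominators it is still 1 - (0.735/0.665)/(0.630/0.630) = -10.5%.

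**The case against.** The strongest reply is that little depends on this. The endpoints are exploratory, SAP 8.1.4 treats significant subgroup results as hypothesis generating, and SAP 8.1.3.5 records that the trial met futility and stopped enrolling. Case numbers per stratum are therefore small and intervals very wide. The size of the error rests on acquisition rates and vaccine effects that the documents do not give. The SAP also compares the proportion colonized between arms at each scheduled visit, including before surgery (6.3.4, 8.1.3.4, Table 25), so a reader can see whether stratum sizes differ. All of this stands and sets the severity. It does not justify calling a post-vaccination swab baseline when a pre-vaccination one exists, and the label does not correct a systematic error.

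Some stronger readings are tempting but not supported:

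- That any effect on carriage biases these endpoints. Under the two-visit definition only acquisition or detection among Visit 1-negative subjects does.
- That reported VE would have opposite signs in the two strata. Only the error component does (step 6).
- That protection through carriage is lost. It shifts into the carrier stratum, and the primary analysis does not condition on colonization.
- That the SAP has no vaccination-time subgroup. Section 8.1.4 lists and defines one, so the gap is a conflict between two lists. Items 8 to 10 are labelled as surgery-time and are not presented as baseline.
- That Visit 1 strata are guaranteed equal. They are balanced in expectation only; chance and per-protocol exclusions remain.

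**Conclusion.** The point holds as a minor one. The baseline definition for the colonization-based VE endpoints includes a post-vaccination measurement, the estimator has no stratum denominators, and the planned h analysis does not reach these endpoints. If SA4Ag reduces acquisition or detection of carriage in Visit 1-negative subjects, VE is too high in carriers and too low in noncarriers. Over the assumed ranges the error is about +1% to +36% and -2% to -20% when true VE is 0, and usually smaller than sampling error. Those ranges also assume equal per-subject risk by status; step 8 shows that selection can make the noncarrier error larger. With no effect on carriage there is no bias.

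A reader might infer that the trial cannot answer its colonization objectives or that its main result is in doubt. The documents support neither: the bias is conditional on an unshown effect, and primary VE, alpha and power do not use colonization status.

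**What to change.** 1. For the efficacy endpoints by baseline colonization, define the stratum from the Visit 1 pre-vaccination swabs only, with the existing window of up to 7 days before vaccination.
2. Reconcile SAP 8.1.4 with 8.2.1 by adding vaccination-time colonization to the efficacy subgroup list.
3. Keep surgery-time status, and any two-visit status, as a subgroup labelled post-vaccination and descriptive. Compute its VE as 1 - hP/(1 - P), with h the number of placebo subjects divided by the number of SA4Ag subjects in the stratum. SAP 8.1.1 now uses follow-up time for h but describes that as a substitution for numbers of subjects. State that this corrects stratum size and not post-vaccination selection.

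The cost is SAP wording and reprogramming, with matching text for Protocol 9.3.4.2. The Visit 1 swabs are already collected from all subjects (Protocol 7.3.4). The downside is fewer subjects classed as positive, because one visit is used instead of two: in the step 3 example, 30% instead of 37% on placebo.
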